Statistical Test Method (continued)	
 • The primary endpoints above will be performed for ICD and CRT-D cohorts combined (primary analysis) as well as for ICD and CRT-D treated subjects separately (for descriptive purpose). • For PM/CRT-P treated subjects, the all-cause mortality free-rate (survival rate) from implant will be calculated as the proportion of actively enrolled subjects who are alive 12 months after implant. The null hypothesis will be rejected and the endpoint considered met if the lower one-sided 97.5% confidence bound for the proportion of subjects with no death is greater than 80.0%. • For Non-device subjects (ESC Guideline 2016 Indicated but not implanted), the all-cause mortality free-rate (survival rate) from enrolment will be calculated as the proportion of actively enrolled subjects who are alive 12 months after enrolment. The null hypothesis will be rejected and the endpoint considered met if the lower one-sided 97.5% confidence bound for the proportion of subjects with no death is greater than 80.0%. • Exploratory analyses for ICD and CRT-D Cohorts combined versus Non-Device Cohort (ESC Guideline 2016 Indicated but not implanted): propensity score matching comparison of all-cause mortality rate and composite rate of HF events between pooled cohorts with device (ICD and CRT-D) versus the Non-Device Cohort regarding 7 risk factors at baseline (NYHA Class III or IV, renal dysfunction [chronically BUN >26 mg/dL / ≥ 9.28 mmol/L], diabetes type I and II, chronic atrial fibrillation [permanent or persisting according to ESC Guideline 2016], prior MI, age >70 years, smoking today or during last 5 years). 
Further details on analytical methods can be found in Section 12 of the CIP

Sample Size Parameters	
ICD Treated Subjects:
 
The minimum required sample size to statistically power the ventricular arrhythmia associated symptoms free-rate through 12 months post implant is 117 subjects. Sample size was calculated assuming a 95.0% ventricular arrhythmia associated symptoms free-rate, a performance goal of 85.0%, one-sided alpha level of 0.025, 90% power, and 20% attrition.

Heart Failure Indication and Sudden Cardiac Death Prevention Trial Japan
Hinode

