Sample Size Parameters (continued)	
Non-device Subjects (ESC Guideline 2016 Indicated but not implanted):
 
The minimum required sample size to statistically power the all-cause mortality free-rate (survival rate) through 12 months after enrolment is 172 subjects. Sample size was calculated assuming a 90.0% all-cause mortality free-rate, a performance goal of 80.0%, one-sided alpha level of 0.025, 90% power, and 20% attrition.
 
The final sample size of 300 for Non-device subjects is higher than that required to power the primary endpoint in order to ensure that there will be a sufficient number of subjects to compare the rate of sudden cardiac death in the non-device cohort with the rate of appropriately treated ventricular arrhythmias or sudden cardiac death in the defibrillator cohort (ICD, CRT-D).
 
In case of low enrollment rates, enrollment may be closed after the statistically required calculated minimum sample size for each cohort.

---	--

3. Table of Contents

1. TITLE PAGE	1
2. SYNOPSIS	6
3. TABLE OF CONTENTS.....	20
3.1. Table of Figures.....	25
3.2. Table of Tables	25
4. INTRODUCTION	26
5. DEVICE DESCRIPTION.....	27
6. STUDY OBJECTIVES	28
7. STUDY ENDPOINTS	29
7.1. Primary Endpoints.....	29
7.2. Secondary Endpoints	29
7.3. Additional Endpoints.....	30
8. STUDY DESIGN	30
8.1. Scale and Duration.....	31
8.2. Treatment Assignment	33
8.3. Justification for the Study Design.....	33
9. SUBJECT SELECTION.....	33
9.1. Study Population and Eligibility.....	33
9.2. Inclusion Criteria	33
9.2.1. General Inclusion Criteria.....	34
9.2.2. Inclusion Criteria for the ICD Cohort.....	35
9.2.3. Inclusion Criteria for the CRT-D Cohort.....	36
9.2.4. Inclusion Criteria for the PM/CRT-P Cohort	37
9.2.5. Inclusion Criteria for the Non-device Cohort (ESC Guideline 2016 Indicated but not implanted)	38
9.3. Exclusion Criteria	39
9.3.1. General Exclusion Criteria	39
9.3.2. Exclusion Criteria for the ICD and CRT-D Cohorts	41
9.3.3. Exclusion Criteria for the PM/CRT-P Cohort	41

9.3.4. Exclusion Criteria for the Non-device Cohort (ESC Guideline 2016 Indicated but not implanted)	41
10. SUBJECT ACCOUNTABILITY.....	41
10.1. Point of Enrolment.....	41
10.2. Withdrawal.....	42
10.3. Subject Status and Classification.....	42
10.4. Enrolment Controls	43
11. STUDY METHODS	43
11.1. Data Collection	43
11.2. Study Candidate Screening	47
11.3. Informed Consent	47

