This is a non-randomized prospective registry study to collect clinical data in the real-life setting in Japan. Enrolled subjects will include those who have been implanted with BSC pacing or defibrillation devices as well as post MI subjects with preserved EF and no device treatment. Subjects will be assigned to one of the 3 following Subject Cohorts according to device implanted:

1. ICD: 117 to 270 subjects
2. CRT-D: 95 to 250 subjects
3. PM/CRT-P: 172 to 200 subjects

A fourth cohort of non-implanted subjects will also be enrolled:

4. Non-device 172 to 300 subjects
(ESC Guideline 2016 Indicated but not implanted)

8.3. *Justification for the Study Design*

The primary objective of this study is to collect clinical event data for selected patient cohorts who are at risk of ventricular tachy-arrhythmias and HF events. In order to obtain “real world” data, the study inclusion/exclusion criteria and follow-up schedule have been written generally enough to allow for study site specific SOC which should accurately capture the clinical data in a “standard” clinical setting. Additionally, by requiring study sites to follow their specific SOC, risk to the subject is minimized because the treatment received by the subject will be similar to the treatment the subject would receive if not participating in the study.

Requiring that all implanted devices be programmed per protocol and the respective BSC IFU, all devices must be intended to be connected to the Latitude system during study duration.

The determination of sample size is provided in Section 12.1.6.

9. Subject Selection

9.1. *Study Population and Eligibility*

Inclusion and exclusion criteria are listed in Sections 9.2 and 9.3 below.

Subjects who are enrolled but later determined to not fulfil all inclusion and exclusion criteria at the time of enrolment will be considered to have incurred a Clinical Investigation Plan (CIP) deviation. These subjects will be withdrawn from the study immediately and will not be included in the planned data analysis.

9.2. *Inclusion Criteria*

All inclusion criteria apply only at the time of enrolment into the study.

If a subject's medical conditions change after inclusion into the study so that one or several of the general inclusion criteria and inclusion criteria of the pertinent cohort are no longer met, the subject remains in the study.

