12.1.1.2. Statistical Methods

When the final study subject reaches the final CIP required follow-up visit, the primary analysis will be performed based on the Kaplan-Meier method for the estimation of the 12-month ventricular arrhythmia associated symptoms free-rate, including the lower 97.5% confidence bound (computed based on log-log methodology). This Kaplan-Meier analysis will begin at the time of implant. Subjects that withdraw consent or are lost-to-follow-up prior to the 12-month endpoint evaluation will be censored at their date of last contact. All subjects actively enrolled will be included in the endpoint analysis.

The null hypothesis will be rejected and the endpoint considered met if the lower 97.5% confidence bound for the ventricular arrhythmia associated symptoms free-rate at 12 months is greater than 85.0%.

Additionally, a Kaplan-Meier survival time-to-event curve along follow-up will be provided.

The primary analysis above will be performed for CRT-D and ICD cohorts combined as well as for ICD treated subjects separately.

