12.1.4.2. Statistical Methods

When the final study subject reaches the final CIP required follow-up visit, the primary analysis will be performed based on the Kaplan-Meier method for the estimation of the 12-month all-cause mortality free-rate (survival rate) including the lower 97.5% confidence bound (computed based on log-log methodology). This Kaplan-Meier analysis will begin at the time of enrolment. Subjects that withdraw consent or are lost-to-follow-up prior to the 12-month endpoint evaluation will be censored at their date of last contact. All subjects actively enrolled will be included in the endpoint analysis.

The null hypothesis will be rejected and the endpoint considered met if the lower 97.5% confidence bound for the all-cause mortality free-rate (survival rate) at 12 months is greater than 80.0%.

Additionally, a Kaplan-Meier survival time-to-event curve along follow-up will be provided.

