12.3. Data Analyses

Exploratory analyses for the pooled ICD and CRT-D Cohorts versus Non-Device Cohort (ESC Guideline 2016 Indicated but not implanted) will be performed using propensity score matching method in order to compare the all-cause mortality rate and the composite rate of HF events between the pooled ICD and CRT-D Cohorts versus the Non-Device Cohort regarding 7 risk factors at baseline (age >70 years, smoking today or during last 5 years, prior MI, diabetes type I and II, chronic atrial fibrillation, renal dysfunction, NYHA Class III or IV).

A propensity matching score will be generated for each subject by logistic regression where the 'device' variable (device implantation Yes/No) is the dependent variable and the

covariates are the 7 risk factors in the model. Each subject in the pooled ICD and CRT-D Cohorts will be matched to a subject in the Non-Device Cohort based on the closest propensity score.

Subjects in the pooled ICD and CRT-D Cohorts will then be compared to those in the Non-Device Cohort before propensity score matching and after propensity score matching for each of the 7 risk factors using the Chi-square test. This technique enables evaluation of the success of propensity matching.

Finally, the all-cause mortality rate and the composite rate of HF events (outcomes) will be compared between the pooled ICD and CRT-D Cohorts and the Non-Device Cohort using the Chi-square test.

The detailed statistical method for propensity score matching will be presented in an SAP.

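### The exploratory device versus Non-device matching needs a replacement rule with a suitable variance, QRS/LBBB in the score, and a common time origin and horizon

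*Combined protocol and SAP*

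**What the plan says.** Section 12.3 labels the comparison exploratory. A logistic model on seven baseline risk factors gives the score, and then "Each subject in the pooled ICD and CRT-D Cohorts will be matched to a subject in the Non-Device Cohort" by closest score. All-cause mortality and the heart failure composite "will be compared between the pooled ICD and CRT-D Cohorts and the Non-Device Cohort using the Chi-square test". The section closes with "The detailed statistical method for propensity score matching will be presented in an SAP". The synopsis (Statistical Test Method) lists the same seven factors.

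Neither place gives a replacement rule, caliper, tie rule, variance method, time origin or horizon. The document supplied holds no further text on the matching.

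Section 8.2 plans 117 to 270 ICD and 95 to 250 CRT-D subjects, and "Non-device 172 to 300 subjects". For the primary endpoints, the ICD text reads "This Kaplan-Meier analysis will begin at the time of implant" (Section 12.1.1.2; Section 12.1.2.2 for CRT-D agrees), while the Non-device text reads "This Kaplan-Meier analysis will begin at the time of enrolment" (Section 12.1.4.2).

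**The concern.** This is the only planned adjusted comparison of device with no device for mortality and heart failure events, since Section 12.3.5 gives multivariable analyses as not applicable. Readers may well lean on it. Three features could mislead them.

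- **Matching and test.** Matching each device subject and treating all matched records as independent cannot both hold when device subjects outnumber controls. A Chi-square counts a control used twice as two people, so it overstates the evidence for a difference.
- **Score.** Seven of the nine predefined risk factors enter. Leaving out LVEF of 35% or less does no harm, because it is an entry condition in all three cohorts. Leaving out QRS/LBBB is different, because QRS helps decide who receives a CRT-D.
- **Time.** A Chi-square on crude proportions ignores unequal follow-up, and nothing says when the clock starts or stops.

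**Working it through.** **Pool sizes.** Table 12.1-1 gives 93, 76 and 137 subjects needed for analysis in the ICD, CRT-D and Non-device cohorts. Dividing by 0.8 for 20% attrition and rounding up gives 117, 95 and 172, as stated. With 172 for PM/CRT-P the total is 117 + 95 + 172 + 172 = 556, also as stated. The device pool at the minimums is 117 + 95 = 212, against 172 controls. The shortfall is 212 − 172 = 40, which is 40/212 = 18.9% of device subjects.

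**Smallest effect of reuse.** Let k be the number of times a control is used. With equal event risk in both groups, the ratio of the true variance to the one the Chi-square assumes is (212 + Σk²)/(2 × 212). The most even pattern uses 40 controls twice and 132 once, so Σk² = 160 + 132 = 292 and the ratio is 504/424 = 1.19. A nominal two-sided 5% test then rejects with probability 2[1 − Φ(1.96/√1.19)] = 7.2%. Direct simulation at a 10% event rate gives 7.0%.

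**Effect if each subject simply takes the closest score.** Assumptions: seven independent binary factors with the same prevalences in both groups (0.35, 0.30, 0.40, 0.35, 0.25, 0.30, 0.45), events at 10% or 15% in both groups, no true effect, and unrestricted reuse.
- With ties broken towards even use, about 128 distinct controls serve and the test rejects about 13% of the time.
- With ties broken at random, about 109 serve and it rejects about 15%.
- On the same matched data, a variance clustered on subject rejects about 5 to 7%.
- Single-use matching within 0.2 SD of the logit rejects 4.4 to 5.4% over the enrolment mixes tried. At 212 v 172 it leaves on average about 52 of 212 device subjects (25%) unmatched.

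**Where reuse is not forced.** At 212 device subjects and 300 controls, also a permitted mix, there are enough controls. Larger mixes depend on the total enrolment cap, which is itself inconsistent: 950 in the synopsis and Sections 8.1 and 10.4, but 900 in Section 12.2.2. No figure here rests on it.

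**QRS.** Section 9.3.2 excludes CRT implanted at a QRS below 130 ms, so every CRT-D subject is at or above 130 ms. These subjects are 95/212 = 45% of the device pool at the minimums. Section 9.2.5 offers two Non-device routes: one requires a wide QRS and the other has no QRS criterion. The distributions may therefore differ, but the documents do not show by how much or in which direction. Table 11.1-1 already requires intrinsic QRS at enrolment.

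**Follow-up.** It runs from about 12 months (Section 11.8; Section 8.1 expects 16) to 34 months. At the protocol's 10% per year, the expected proportion dead is 10.0% at 12 months and 1 − 0.9^(34/12) = 25.8% at 34 months. A crude proportion thus depends strongly on exposure. It biases the comparison only if exposure differs between the groups.

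**Time origin, if the primary origins were carried over.** A device subject enrolled 45 days after implant can contribute a death only in the remaining 320 days: 1 − 0.9^(320/365) = 8.8%, against 10.0% for a full year from enrolment. That is at most 1.2 points. Averaged over an assumed uniform delay of 0 to 45 days it is about 0.6 points.

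**The case against.** The strongest reply is that the analysis is exploratory and that replacement, caliper, variance and horizon are just the detail left to the SAP. No decision rule depends on this test. That limits the weight of the point, but Section 12.3 has already fixed one match for each device subject, the seven covariates and the Chi-square. An SAP that only adds detail would inherit them. The time origin and horizon are different: there the section is silent and has made no choice.

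Several stronger readings are tempting and are not supported:

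- A reader might infer that the shortage of controls itself produces a 13 to 15% error rate. It does not. The forced 40 repeats give about 7%; the higher figure comes from unrestricted reuse, which the plan does not specify.
- A reader might infer that reuse is unavoidable at any enrolment. At 212 v 300 it is not.
- A reader might infer that device subjects will be counted from implant. Section 12.3 does not say so. Reportable events are collected only after consent (Section 10.1) and the consent date defines enrolment (Section 11.1), so common observation starts there.
- A reader might infer that accrual periods will differ, because "enrollment may be closed after the statistically required calculated minimum sample size for each cohort" (synopsis, Sample Size Parameters). That sentence applies only in case of low enrolment, and Sections 8.1 and 10.4 describe a study-wide closure. Any accrual effect is conditional on accrual actually differing.
- A reader might infer that omitting QRS favours one group. Since one Non-device route itself requires a wide QRS, no direction can be given.

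**Conclusion.** The point holds as a specification gap in an exploratory analysis, of minor to moderate severity. The conflict between matching each device subject and testing by an ordinary Chi-square is arithmetic at the enrolment minimums: at least 40 reuses or at least 40 unmatched subjects. The resulting error rate, about 7% at the least and about 13 to 15% under unrestricted closest-score reuse, rests on assumed prevalences, event rates and no confounding. QRS/LBBB is a relevant omission with no derivable size. The time-origin effect is at most 1.2 points, and arises only if the primary origins are carried over. No primary endpoint, hypothesis or sample size changes.

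**What to change.** State in Section 12.3 or the SAP:

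1. **Matching.** Replace the rule that each device subject is matched with 1:1 matching without replacement within a caliper (for example 0.2 SD of the logit), report the unmatched subjects and name the target population. Alternatively keep reuse, with matching weights and a variance clustered on subject.
2. **Score.** Add QRS duration and LBBB, using the intrinsic enrolment values.
3. **Time.** Use enrolment as the common origin, and compare the matched sample by Kaplan-Meier and Cox methods with robust variance, or at a fixed 12-month horizon.

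The cost is wording and modest programming, with no new data. Single-use matching leaves some device subjects unmatched (about 25% at the minimums in the simulation) and may change the target population. Reuse with a clustered variance keeps them all but gives a wider interval than the planned test implies. Adding QRS may reduce overlap further, which should be reported.

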12.2.3. Descriptive Statistical Methods

Descriptive statistical methods will be used to summarize the data from this study, with hypothesis testing performed for the primary endpoints. Unless otherwise stated, all statistical testing will be one-sided and will be performed using a significance (alpha) level of 0.025.

Continuous variables as a minimum will be described by number of non-missing observations (n), arithmetic mean (Mean), SD, minimum (Minimum), median (Median), and maximum (Maximum). One additional decimal point for mean and median and 2 additional decimal points for SD will be used.

Categorical variables will be presented using the number of non-missing observations (n) or the number of subjects in the population (N) as applicable and percentages (%). Percentages will be rounded to one decimal place. Unless otherwise stated, two-sided 95% confidence intervals (CIs) will be provided when relevant. The two-sided 95% CI will be presented as it provides the one-sided 97.5% lower (resp. upper) limit when the upper (resp. lower) bound is ignored to assess superiority.

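### Section 12.3 judges the propensity matching only by Chi-square tests, which can miss material residual imbalance at the planned cohort sizes

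*Combined protocol and SAP*

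**What the plan says.** Section 12.3 plans "Exploratory analyses for the pooled ICD and CRT-D Cohorts versus Non-Device Cohort" for all-cause mortality and the composite of heart failure events. The propensity score comes from a logistic regression for device implantation, in which the "covariates are the 7 risk factors in the model". Each device subject "will be matched to a subject in the Non-Device Cohort based on the closest propensity score". No caliper, replacement rule or matching ratio is stated.

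The cohorts are then compared before and "after propensity score matching for each of the 7 risk factors using the Chi-square test". The section gives this comparison its role in one sentence: "This technique enables evaluation of the success of propensity matching". It names no standardised difference, no p-value or other limit at which a factor counts as balanced, and no step to take if balance is poor. The two outcomes are compared by an unadjusted Chi-square test.

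Section 12.3 ends with a deferral: "The detailed statistical method for propensity score matching will be presented in an SAP". The text available contains no further matching detail. Section 12.2.3 sets the default that, unless otherwise stated, "all statistical testing will be one-sided and will be performed using a significance (alpha) level of 0.025".

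**The concern.** Whether matching worked is a question about the subjects who were matched: how far apart are the two groups on each factor? A Chi-square p-value answers a different question, whether the difference is larger than sampling error would produce at that sample size. With few pairs, a large difference passes. With many pairs, a trivial one fails.

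This matters because device choice is not randomised. Sections 5 and 8 leave it to the physician, so implanted subjects and those with an indication but no device may differ in prognosis. The outcome test is unadjusted, so the balance check is the only stated safeguard on the matched comparison. If it is insensitive, a comparison that is still confounded can be reported as matched.

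**Working it through.** **Inputs from the plan.** Table 12.1-1 sets the Non-device minimum at 172, and section 8.2 gives the range 172 to 300. The figure of 172 reproduces. An exact binomial test of 80% against 90% at one-sided 0.025 needs 137 subjects (reject at 119 or more survivors; alpha 0.0245; power 91.0%), and 137/0.80 = 171.25, rounded up to 172. The plan gives no figure for the balance test itself.

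**Assumptions.** Matching is 1:1 without replacement, so the Non-device cohort caps the pairs at 172 to 300. The level is two-sided 5%. The groups are treated as independent. Risk-factor prevalences are not in the documents; 40% v 50% and 40% v 45% are illustrations.

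**Standardised difference.** d = |p1 − p2| / √[(p1q1 + p2q2)/2], where q = 1 − p.
- 40% v 50%: 0.10/√[(0.24 + 0.25)/2] = 0.10/0.495 = 0.20
- 40% v 45%: 0.05/√[(0.24 + 0.2475)/2] = 0.05/0.494 = 0.10

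**Probability that the test flags the difference with n pairs.** Φ[(|p1 − p2| − 1.96·s0)/s1], with s0 = √[2p̄(1 − p̄)/n] and s1 = √[(p1q1 + p2q2)/n]. The opposite tail adds at most 0.002.

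| True difference | n pairs | s0 | s1 | z | Flagged |
|---|---|---|---|---|---|
| 40% v 50% | 172 | 0.0536 | 0.0534 | −0.10 | 46% |
| 40% v 50% | 300 | 0.0406 | 0.0404 | 0.50 | 69% |
| 40% v 45% | 172 | 0.0533 | 0.0532 | −1.02 | 15% |
| 40% v 45% | 300 | 0.0404 | 0.0403 | −0.72 | 24% |

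The result depends little on prevalence. With a lower prevalence of 20%, 30% or 40% and d fixed at 0.20, the test flags about 45% at 172 pairs and 68% at 300.

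**Largest observed difference that stays above p = 0.05.** This needs no power model.
- 172 pairs: 69/172 (40.1%) v 87/172 (50.6%), 10.5 points, d = 0.21
- 300 pairs: 120/300 (40.0%) v 143/300 (47.7%), 7.7 points, d = 0.155

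**Same imbalance, different answer.** For 30% v 40% (d = 0.21), χ² = n(0.10)²/(2 × 0.35 × 0.65) = n × 0.01/0.455.
- 300 pairs: χ² = 6.59, p = 0.010
- 172 pairs: χ² = 3.78, p = 0.052
- 100 pairs: χ² = 2.20, p = 0.14

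**The opposite error.** With seven independent tests at 5% and perfect balance, the chance of at least one p<0.05 is 1 − 0.95⁷ = 1 − 0.698 = 30%.

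**The case against.** The strongest reply is that little depends on this check. The comparison is exploratory, no primary endpoint or sample size uses it, and matching detail is left to an SAP. Section 12.2.3 has categorical variables reported as counts and percentages, so a reader would see 40% v 50% directly. The bias may also be modest. A factor assumed to double mortality and left at 50% v 40% shifts the mortality ratio by 1.5/1.4 = 1.07. At 10% mortality in each group of 172, the 95% interval around a ratio of 1 is exp(±1.96 × √[2 × 0.9/(172 × 0.1)]), or about 0.53 to 1.89. All of this stands, and it limits the weight of the point. The deferral does not remove it, because section 12.3 has already named the Chi-square test as the measure of success.

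Three stronger readings are tempting, and the documents do not support them.

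- *Shrinkage from matching is the main cause.* Within one enrolment scenario the loss is small. For 40% v 50% at minimum enrolment, the chance of flagging falls from 50% (212 v 172) to 46% (172 pairs). At the maximum cohort sizes it falls from 79% (520 v 300) to 69% (300 pairs), and that scenario cannot occur with the pacemaker cohort at its minimum: 520 + 300 + 172 = 992, above the cap of 950. The weakness is low sensitivity at the planned size, already present before matching.
- *The default alpha makes imbalance harder still to flag.* The 0.025 in section 12.2.3 is one-sided, and that section itself ties it to the two-sided 95% interval. The matching level for a two-sided Chi-square test is 5%.
- *A poorly balanced match will be declared balanced.* No cut-off or declaration rule is stated, and a difference of 0.20 is still flagged in nearly half of cases at 172 pairs. It can be passed as balanced; it need not be.

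**Conclusion.** The point holds as a weakness of method in an exploratory analysis. The only named diagnostic would miss a standardised difference of 0.20 about 54% of the time at 172 pairs and 31% at 300. It would miss one of 0.10 about 85% and 76% of the time. It would also raise a false alarm on at least one factor in about 30% of perfectly balanced matchings.

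These figures rest on the assumed prevalences, a two-sided 5% level, 1:1 matching without replacement, independent groups and, for the 30%, independent tests. A caliper would reduce the pairs and lower sensitivity further; matching with replacement would change the count in a way the plan does not define. The exposure is confined to how the device v Non-device results for mortality and heart failure events are described.

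**What to change.** In section 12.3 and the SAP, replace the Chi-square balance check with absolute standardised differences before and after matching. Show them for the seven factors and for other baseline variables already collected, such as LVEF, QRS width and morphology, and medication in the section 12.3.6 list. Preset the limit; 0.10 is conventional but comes from outside the documents, so the SAP should give it as a choice with a reason.

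If any factor exceeds the limit, add a sensitivity analysis of the outcome adjusted for that factor, and say so when the matched result is reported. Section 12.3.5 now marks multivariable analyses as not applicable and would need an exception.

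The cost is protocol and SAP wording plus a small amount of extra exploratory analysis, since section 12.3 now plans only a Chi-square outcome test. No extra data, visits or subjects are needed.
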